This group of patients was chosen as the population for the primary analysis for several reasons. First, this group includes those patients who will benefit most from a reduction in delay time by virtue of faster receipt of medical services. Hence, the presence of a reduction in delay should be established in this group, rather than in the larger group of patients that also includes those who have non-cardiac causes of their symptoms. Second, patients with cardiac diagnoses will be more stable across communities and over time than the larger group of patients with symptoms suggestive of acute IHD. Third, patients with cardiac diagnoses will be identified more uniformly and consistently across Field Sites and over the study period. Fourth, sufficient numbers are expected for the purposes of statistical precision and power to adequately examine differences in the primary trial outcomes between intervention as compared to control communities.

A 30-40 minute net reduction in median delay time is considered to be a clinically meaningful intervention effect; thus, in the primary analysis, we will examine delay time as a continuous variable. However, it is also important to increase the percentage of patients who arrive at the hospital within six hours of onset of acute

symptoms, early enough to be treated within the optimal window for receipt of thrombolytic therapy or immediate PTCA. Thus, we will also examine delay time classified as a dichotomous variable (i.e. the proportion of cases delaying < six hours vs $\geq six$ hours).

G. Secondary Outcomes

The following secondary outcomes will be measured and analyzed. The definition and measurement of each outcome is described in Section VII.

- 1. Secondary Populations and Subgroups
- a. The primary intervention effect will be examined among *patients with* diagnosed MI. Since this subgroup includes the vast majority of patients eligible for thrombolytic therapy and/or immediate PTCA, we will examine the intervention effect on their prehospital time delays.
- b. The primary intervention effect will be examined in patients seen in the ED for chest pain and admitted for possible acute ischemia. These patients have been identified by physicians as warranting further diagnosis and/or treatment, and they are targets of the intervention.

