An important subgroup of the primary population for whom we would like to assess the intervention effect is those patients with confirmed MI. Additional subgroups are defined by the individual level covariates \mathbf{x} (age, gender, and history of MI). Additional subgrouping variables are listed in Section IV. The primary analytic method will be carried out in each subgroup defined by these variables.

Differential intervention effects among subgroups will be tested using model (3), except that instead of $\beta + \lambda_i + Q_{j(i)} + \tau_k + V_{jk(i)}$, the coefficient in front of *t* will be $\beta + \lambda_i + Q_{j(i)} + \tau_k (1 + \mathbf{f}^T (\mathbf{x} - \overline{\mathbf{x}})) + V_{jk(i)}$. A significant value of a φ coefficient (using a two-tailed test at $\alpha = .05$) indicates a differential effect of intervention for different values of covariates. If this happens, the model will be used to compute estimates of the difference in slopes between intervention and control communities for the different subgroups defined by the covariate. The other covariates will be set to their average values.

5. Secondary endpoints

Several secondary analyses will attempt to assess the clinical consequences of decreased delay time. The hypotheses, discussed in Section X., are that reducing delay time will result in

- a. more frequent delivery of early revascularization;
- b. less severe disease;
- c. shorter hospitalization;
- d. lower mortality from MI and acute ischemia; and
- e. increased emergency department utilization (both appropriate and inappropriate).

Among the measures addressing these outcomes, many are proportions; for example,

a. proportion of primary patients who receive thrombolytic therapy or PTCA;

- b. proportion of primary patients who die in the hospital;
- c. proportion of primary patients who incur ventricular fibrillation within 24 hours of admission;
- d. proportion among ED patients with chest pain who turn out not to have MI or unstable angina.

For these dichotomous endpoints, the two-step procedure beginning with (4) will be used, with p denoting the probability of interest (for example, the probability that a patient will die in the hospital).

Other secondary questions are addressed by continuous measures; for example,

- a. average daily number of patients presenting in the emergency department with chest pain;
- b. average daily number of 911 calls for chest pain;

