where $\rho + \rho^*$ is the correlation between two subgroup slopes drawn from the same community. ρ^* may be considered the *additional* correlation attributable to two slopes' coming from the same community, rather than merely from the same matched pair. It is reasonable that ρ^* should be at least as large as ρ . To be conservative we shall assume ρ^* equal to ρ .

The contrast $\overline{d'}$ serves to test the hypothesis of Intervention × Subgroup interaction. The detectable slope differential between complementary subgroups is

$$\Delta'\beta = SE(\overline{d'})(t_{\alpha/2} + t_{1-\Pi}).$$

In this case the t-statistic has 9 df.

D. Detectable Effect, Binary Endpoints

Many of the secondary endpoints of REACT are yes/no variables, such as receipt of thrombolytic therapy or use of 911 service. Accordingly the power analysis for secondary variables will be presented in terms of dichotomous outcomes.

A statistical model for binary endpoints can be formulated similarly to that presented above for the continuous, log-transformed primary endpoint. The prevalence of the binary endpoint at any point in time will be denoted p. To cover the wide range of binary endpoints of interest, the calculation has been performed for p=0.01, 0.05, 0.10, 0.20, 0.30, and 0.50. The numerical results are identical for the complementary cases p=0.99, 0.95, 0.90, 0.80, and 0.70.

The transformed prevalence y = logit(p) = ln[p/(1-p)] is assumed to follow an approximately linear time course:

$$y(t) = y(0) + \beta t$$
, $0 \le t \le 1.5$ yr.

The slope estimate b is again the community-level measure of interest. As derived from simple logistic regression, the variance of b is approximately $1/\pi(1-\pi)KV_t$, where π is the "average" prevalence over the time range (105).

The mean difference between Intervention and Control slopes has variance identical to the continuous case except for substitution of $1/\pi(1-\pi)$ for σ^2 . The random variance component σ_{β}^2 is related to the binary endpoint by $R_{\beta} = e^{2\sigma_{\beta}L}$, R_{β} being the Odds Ratio for the outcome in a community at the outer 95% limit of slope variation as compared to a community in the center of the slope distribution at the end of the *L*-year trial. The values $R_{\beta} = 1.05$ and 1.15 were used for sensitivity analysis as in the previous case.

The detectable slope difference,

$$\Delta\beta = SE(\overline{d})(t_{\alpha/2} + t_{1-\Pi}),$$

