Table 10 shows the detectable levels of effect modification that might be ascribable to subgroup membership. These are second-order contrasts in delay-time slope between complementary subgroups. Again the "best" and "worst" parameter combinations are examined. These effects will be difficult to detect, as is often the case with subgroup comparisons. Even in the best case of parameter values, with the optimal subgroup split for precision (50/50), the second-order contrast would have to be 30% in relative reduction, or 44 min. in abolute reduction, to be detected with 80% power. This is an effect modification larger than the anticipated average effect itself, and is not likely to occur even in a highly responsive subpopulation such as medical professionals or patients with prior history of coronary disease.

Secondary endpoint effects are shown in Table 11, again at levels detectable with 80% power. This calculation was performed for binary endpoints, which dominate the list of secondary outcomes of interest in the primary population. The "best-case" and "worst-case" variance parameters are used with the expected sample size (K=600 per community).

The most readily detectable effects are perturbations of an initial 50% prevalence; relative risk of 1.17 (best case) or 1.18 (worst case between the expected full samples in REACT intervention and control communities will be demonstrable with 80% power. For less prevalent events (or more prevalent ones), the relative risk would have to be closer to 1.5 to stand a good chance of detection, and for rare (or common) events an extreme effect, on the order of RR=5, would be necessary to ensure a high likelihood of detection.

Binary endpoints are examined for subsamples as well in Table 11. Because the detectable effects for the full sample appear insensitive to variance parameters, only the "best" case is shown for subsamples. Subsample sizes are examined for K=200 and K=100, as are planned for random-sample telephone surveys, and for the "pessimistic" full-sample case of K=400. The detectable effects for these smaller samples are considerably larger than for the full sample, with RR in the range of 1.5-3.0 for common events and above 5.0 for rarer events.

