Table 10.	Detectable Reduction in Delay Time, Secondary Comparison Between	
	Complementary Subgroups*	

	Subgroup split (%)	Relative (%)	Absolute	e (min)	
			M=2.5 hr	M=3 h	
Best case:	10/90	48	72	86	
$R_{\beta} = 1.05$	20/80	39	58	69	
ρ=0.4	30/70	35	52	62	
	40/60	33	49	59	
	50/50	32	48	58	
Worst case:	10/90	49	73	87	
$R_{\beta} = 1.15$	20/80	40	60	71	
ρ=0.0	30/70	36	54	65	
	40/60	34	52	62	
	50/50	34	51	61	

Sample per		Prevalence (%)		Detectab	le effects	
community (K)			PLo (%)	P _{HI} (%)	OR	RR
600	Best case:	1 or 99	0.2	4.7	4.87	4.76
	$R_{\beta} = 1.05$	5 or 95	2.5	9.8	2.06	1.98
	ρ=0.4	10 or 90	6.2	15.8	1.69	1.60
		20 or 80	14.4	27.1	1.48	1.37
		30 or 70	23.3	37.7	1.41	1.27
		50	42.2	. 57.8	1.37	1.17
	Worst case:	1 or 99	0.2	4.7	4.88	4.77
	$R_{\beta} = 1.15$	5 or 95	2.5	9.8	2.07	1.99
	ρ=0.0	10 or 90	6.1	15.9	1.70	1.61
		20 or 80	14.3	27.2	1.50	1.38
		30 or 70	23.1	37.9	1.43	1.28
		50	41.9	58.1	1.39	1.18
400	Best case:	1 or 99	0.1	6.6	6.96	6.73
	$R_{\beta}=1.05$	5 or 95	2.1	11.3	2.48	2.31
	ρ=0.4	10 or 90	5.5	17.5	1.90	1.78
		20 or 80	13.4	28.8	1.62	1.47
		30 or 70	21.9	39.5	1.52	1.34
and the second second		50	40.5	59.5	1.47	1.21
200	Best case:	1 or 99	0.1	13.6	15.53	14.45
	$R_{\beta} = 1.05$	5 or 95	1.5	15.6	3.50	3.24
	ρ=0.4	10 or 90	4.3	21.6	2.42	2.25
		20 or 80	11.2	33.1	1.98	1.72
		30 or 70	19.1	43.8	1.81	1.51
		50	36.7	63.3	1.73	1.31
100	Best case:	1 or 99	0.0	32.8	48.39	39.66
	$R_{\beta} = 1.05$	5 or 95	0.9	23.6	5.88	5.16
	ρ=0.4	10 or 90	3.0	28.7	3.62	3.10
		20 or 80	8.7	39.6	2.63	2.13
		30 or 70	15.6	49.9	2.32	1.79
		50	31.6	68.4	2.16	1.47

Table 11. Detectable Effects on Secondary Binary Endpoint, Primary Population*

*80% power, 5% Type I error (two-sided).

Figure 7. Distribution of delay time (T). Left: In natural units, T is assumed log-normal, with median M and 95% of residual variation lying between M/R and MxR. Right: $\log_{10}T$ is normally distributed with mean $\mu = \log_{10} M$ and standard deviation $\sigma = 1/2\log_{10} R$; 95% of residual variation lies in the range $\mu \pm 2\sigma$.

Figure 8. Random variation in slope results in R_{β} -fold variation in delay time at the end of the trial (95% limits), given the same starting point. Parametrization is $R_{\beta}=10^{2\sigma\beta L}$, where L is length of trial and σ_{β}^{2} is variance of slopes.

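### Table 11 gives one set of limits and risk ratios for each prevalence and its complement, but only the odds ratio is shared; the printed limits and RR are wrong for prevalences of 70 to 99%

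*Protocol*

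**What the plan says.** Appendix C.D models a binary endpoint on the logit scale. It says that "the calculation has been performed for p=0.01, 0.05, 0.10, 0.20, 0.30, and 0.50", and then: "The numerical results are identical for the complementary cases p=0.99, 0.95, 0.90, 0.80, and 0.70".

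The appendix defines p_Lo and p_Hi as the end-of-trial prevalences just detectable below and above the starting prevalence p. It defines RR as the square root of p_Hi/p_Lo, described as close to p_Hi/p and to p/p_Lo.

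Table 11 labels its rows 1 or 99, 5 or 95, 10 or 90, 20 or 80, 30 or 70, and 50. Each row has a single p_Lo, p_Hi, OR and RR. Appendix C.E then interprets the RR for common as well as rare events. It says that less prevalent events, or more prevalent ones, need an RR closer to 1.5, and that "for rare (or common) events an extreme effect, on the order of RR=5, would be necessary to ensure a high likelihood of detection".

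**The concern.** Swapping p for 1 − p exchanges the event and the non-event. The odds ratio is only inverted by this, so its size is the same. The prevalence limits and the risk ratio are not preserved. A row labelled 20 or 80 with limits of 14.4% and 27.1% cannot describe an endpoint that starts at 80%, because the limits do not contain the starting value.

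Table 11 is the Protocol's only detectable-effect table for binary endpoints, which Appendix C.E says dominate the secondary outcomes. For a common endpoint, a reader is told to expect a far larger RR than the design needs. The direction is also reversed: above 50% the detectable RR falls towards 1 as prevalence rises, whereas the printed RR climbs towards 5.

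The endpoint most plausibly affected is the one in Section IV.F, "the proportion of cases delaying < six hours vs" six hours or more.

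**Working it through.** **Inputs (Section X.B, Appendix C, Table 8).** J = 10 pairs; L = 1.5 yr; V_t = 459/1936 = 0.237 yr²; K = 600 per community; best case R_β = 1.05 and ρ = 0.4; 80% power, two-sided 5%. The average prevalence π is set equal to p.

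**Formulas (Appendix C.D).**
- σ_β = ln(R_β)/(2L) = ln(1.05)/3 = 0.0163
- SE² = 2σ_β²(1 − ρ)/J + 2/[p(1 − p)·K·V_t·J]
- Δy = L × (sum of quantiles) × SE, and OR = exp(Δy)
- p_Lo and p_Hi = inverse logit of (logit p − Δy) and (logit p + Δy)
- RR = √(p_Hi/p_Lo)

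**Reproducing the table.** With p = 0.20, SE² = 0.00003 + 0.00879, so SE = 0.0939. With normal quantiles (1.960 + 0.842 = 2.802), Δy = 1.5 × 2.802 × 0.0939 = 0.395. Hence OR = 1.48, the limits are 14.4% and 27.1%, and RR = √(27.06/14.42) = 1.37, all as printed. Used this way, the formulas reproduce all 30 rows at p = 1 to 50%, apart from two OR cells (K = 400 at 5%, K = 200 at 10%). The printed figures therefore belong to the low-prevalence member of each row.

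**The complementary case.** With p = 0.80, p(1− p) is again 0.16, so Δy = 0.395 and OR = 1.48. But logit p is now +1.386, so the limits are 72.9% and 85.6%, and RR = √(85.58/72.94) = 1.08. In general the limits become 100 − p_Hi and 100 − p_Lo.

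| p | OR | Printed limits | Correct limits | Printed RR | Correct RR | p × printed RR |
|---|---|---|---|---|---|---|
| 70% | 1.41 | 23.3 / 37.7 | 62.3 / 76.7 | 1.27 | 1.11 | 89% |
| 80% | 1.48 | 14.4 / 27.1 | 72.9 / 85.6 | 1.37 | 1.08 | 110% |
| 90% | 1.69 | 6.2 / 15.8 | 84.2 / 93.8 | 1.60 | 1.06 | 144% |
| 95% | 2.06 | 2.5 / 9.8 | 90.2 / 97.5 | 1.98 | 1.04 | 188% |
| 99% | 4.87 | 0.2 / 4.7 | 95.3 / 99.8 | 4.76 | 1.02 | 471% |

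As an increase, the printed RR is impossible for 80 to 99%. As a decrease it is not excluded, but it does not match the printed OR: 80%/1.37 = 58.4%, which is an odds ratio of 4/(0.584/0.416) = 2.85, not 1.48.

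The other blocks have the same fault. At 80% the printed RRs of 1.38 (K = 600, worst case), 1.47 (400), 1.72 (200) and 2.13 (100) should be 1.09, 1.10, 1.15 and 1.23. At K = 200 and 100 the 70% row also exceeds 100% (70 × 1.51 = 106%; 70 × 1.79 = 125%).

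**The text in Appendix C.E.** An increase by RR 1.5 is impossible for any p above 1/1.5 = 67%, which covers every complementary prevalence listed. At 99% the largest possible increase is 1/0.99 = 1.01.

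**Illustration: arrival within six hours.** The Protocol states no expected proportion. As an assumption, take its log-normal model with R = 9, so σ = log10(9)/2 = 0.477, and P(T < 6 h) = Φ[log10(6/M)/0.477]. The detectable levels are for K = 600, best case.

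| Starting median M | P(T < 6 h) | Detectable upper level (RR) | With t on 9 df | After 30 min fall | After 40 min fall |
|---|---|---|---|---|---|
| 2.5 h | 78.7% | 84.5% (1.09) | 85.1% | 84.1% | 86.0% |
| 3.0 h | 73.6% | 80.0% (1.10) | 80.6% | 78.7% | 80.5% |

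**Quantiles.** Appendix C.B states Student t with 9 df (sum 3.146), while Table 11 matches normal quantiles. That is a separate matter. With t on 9 df the RRs at 70, 80, 90, 95 and 99% are 1.12, 1.09, 1.06, 1.05 and 1.03, so this point does not depend on the choice.

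**The case against.** The strongest reply is that this is a labelling slip. Binary endpoints are analysed on the logit scale, where p and 1 − p are equivalent, and the printed OR serves both. A statistician can recover the limits by subtracting from 100, or read the row as describing the non-event. The summary in Appendix C.E, that power is good unless prevalence is extremely high or low, holds on the OR scale. Sample size was fixed in advance and no design decision rests on these cells.

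The part about the OR, the design and the primary analysis stands. The non-event reading does not rescue the text: the Protocol never states it, and Appendix C.E applies the RR to the common event itself.

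Four stronger readings are tempting but not supported.
- **The table makes an effect on six-hour arrival impossible.** The prevalence is derived, not stated. At a 2.5 h median the nearest row (80%) does imply 78.7 × 1.37 = 108%. At 3 h the nearest row (70%) implies 73.6 × 1.27 = 93%, which is wrong but possible. Section XI.B.2.c also models arrival within four hours after dichotomising at six, so the endpoint itself needs settling.
- **The Protocol writes that endpoint off.** It does not; 74 to 79% is not an extreme prevalence in its own summary.
- **The corrected table shows a 30 to 40 min fall to be detectable.** A 30 min fall is just short of the detectable level at both medians. A 40 min fall exceeds it with normal quantiles, but with t on 9 df it just misses at 3 h (80.5% against 80.6%).
- **The 30 or 70 row can be applied to the "proportion among ED patients with chest pain who turn out not to have MI or unstable angina".** Table 11 concerns the primary population, which is a different denominator.

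**Conclusion.** The point holds in this form. The claim of identical results is true for the OR only, and p_Lo, p_Hi and RR in Table 11 are wrong for every 70 to 99% case in every block. At K = 600, best case, the RR is overstated from 1.27 against 1.11 at 70% up to 4.76 against 1.02 at 99%. Both statements in Appendix C.E on the RR needed for common events are wrong as written.

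The recalculation rests only on the Protocol's formulas and parameters, with the normal quantiles that reproduce the table. The six-hour figures rest additionally on the assumed log-normal model and are illustrative. The consequence is confined to the stated detectable effects for common binary secondary endpoints.

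**What to change.** - In Appendix C.D, limit the statement of identity to the odds ratio.
- In Table 11, print separate p_Lo, p_Hi and RR for p = 0.70, 0.80, 0.90, 0.95 and 0.99 in all five blocks, using whichever quantile the table finally adopts.
- In Appendix C.E, remove the references to more prevalent and to common events from the RR 1.5 and RR 5 statements, or restate both as odds ratios.
- Optionally, give the detectable change in percentage points for arrival within six hours, with the assumed starting proportion stated.

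The cost is 25 recalculated table rows from existing formulas and three edited sentences. No data collection, design or analysis changes.

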The effect of intervention on reducing delay time will be declared significant if the two-tailed significance of the τ_k term is less than 0.05. This model is comprehensive enough to include the most important factors related to delay time, without being overly complicated.

- b. A simpler two stage procedure will be performed in which the model in the first stage will be identical to (1), except there will be no adjustment for covariates. That is, the term $\mathbf{q}^T(\mathbf{x} \overline{\mathbf{x}})$ will be dropped from (1). Other than this change the analysis will be conducted exactly as in the primary analysis.
- c. A further analysis will dichotomize delay time into \leq six hr. vs. \geq six hours. The result will be correlated binary data because some patients may have more than one observation. The Generalized Estimating Equation (GEE) approach (105) with an exchangeable working correlation matrix will be used to model the logit of p = the probability of arriving within 4 hours:

$$\ln\left(\frac{p}{1-p}\right) = \mu_i + \theta^T (\mathbf{x} - \overline{\mathbf{x}}) + \beta_i t + \varepsilon_{ijk}$$
(4)

The terms on the right side of (4) are as defined after (1), and ln denotes the natural logarithm. The estimates, b_i , of the slopes β_i , will be computed in each community. The 10 intervention slopes will be compared to those of the matching control communities using a two-tailed, paired t-test at α =0.05.

3. Secondary definitions of delay time

The same analysis as for the primary endpoint will be conducted in a random sample of the primary population, using data collected by telephone interview and record abstraction, for alternative definitions of delay time, as follows.

- a. Time from onset of symptoms to when emergency care is sought. Because this could be 0, log(delay+.1 hr) will be used in the analysis.
- b. Time from onset of symptoms to treatment by emergency personnel (including ambulance personnel).
- c. Time from onset of symptoms to "definitive treatment" among those who receive definitive treatment.
- 4. Analysis of delay time in secondary populations

The intervention effect on delay time will be assessed in a random sample of patients presenting at the ED with chest pain, but not admitted to the hospital. The same primary analysis that was used for the primary population will be used for this population.

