$$SE^{2}(\overline{d}) = V(\overline{d}) = \frac{2\sigma_{\beta}^{2}}{J}(1-\rho) + \frac{\sigma^{2}}{V_{t}J^{2}}\sum_{j=1}^{J} \left[K_{j,Intervention}^{-1} + K_{j,Control}^{-1}\right].$$

The primary null hypothesis of the REACT trial is that the true mean difference between Intervention and Control slopes, $\Delta\beta = \langle \beta_{Intervention} \rangle - \langle \beta_{Control} \rangle$, is zero. The

alternative hypothesis is that $\Delta\beta \neq 0$; this is a two-sided alternative because it is conceivable (though not likely) that the REACT Intervention could prolong the average delay time.

The primary hypothesis will be tested with the conventional critical value (Type I error rate) of $\alpha=5\%$ (two-sided), using a paired *t*-test on the values of *d*, or, equivalently, using a mixed-model ANOVA with REACT group as a fixed effect (1 df). Using the *t*-test formulation, the smallest effect detectable with a specified level of power Π is given approximately by

$$\Delta\beta = SE(\overline{d})(t_{\alpha/2} + t_{1-\Pi}),$$

where t_0 demarks the specified upper tail area of the central Student distribution. The degrees of freedom for t are J-1=9. (In the equivalent ANOVA formulation, denominator df for the Intervention effect are [Communities - (Treatment Groups-1) - (Sites-1) - Sites \times (Pairs per site-1) - 1] = 20 - 1 - 4 - 5 $\times 1 - 1 = 9$.)

Power has been fixed at Π =80% for the primary analysis on the premise that a largescale trial can afford no more than 1 chance in 5 of achieving a result and then failing, because of random chance alone, to prove its success to the scientific community. For secondary populations and endpoints, the calculations have likewise been performed at 80% power.

It is desirable to address the detectable effect on delay time directly, rather than indirectly through the detectable slope difference. Slope is related to the net end-trial effect on delay time as follows. After L=1.5 yr of intervention, the difference in mean log delay time between Intervention and Control communities will be $\Delta y = L\Delta\beta$. The corresponding effect on the median delay time will be a multiplicative reduction by a factor of $10^{-L\Delta\beta}$, or

Relative reduction = $100\% \times (1 - 10^{-L\Delta\beta})$,

Absolute reduction = $M \times (1 - 10^{-L\Delta\beta})$,

where M is the median delay time at the end of the trial in the Control communities.

C. Detectable Effect, Secondary Populations

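### Table 11 uses normal quantiles where the protocol prescribes t on 9 df, so the binary secondary effects listed at 80% power have about 70%

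*Protocol*

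**What the plan says.** Appendix C, Section B sets the smallest detectable slope difference equal to the standard error of the mean pair difference times the sum of two upper-tail Student t quantiles, one for α/2 and one for 1 − power. It adds: "The degrees of freedom for t are J-1=9". Section D repeats the same expression, in the same t notation, for binary outcomes. It changes only the residual variance, from σ² to 1/[π(1−π)].

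The planned test agrees with this. Section XI.B.5 states: "For these dichotomous endpoints, the two-step procedure beginning with (4) will be used". The procedure under equation (4), in Section XI.B.2.c, ends by comparing the 10 intervention slopes with those of the "matching control communities using a two-tailed, paired t-test at" α = 0.05.

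On the power level, Appendix C, Section B says: "For secondary populations and endpoints, the calculations have likewise been performed at 80% power". The results are in "Table 11. Detectable Effects on Secondary Binary Endpoint, Primary Population", whose footnote gives 80% power and a two-sided 5% error rate. The text of Section E takes from it, for 50% prevalence, a "relative risk of 1.17 (best case) or 1.18 (worst case between the expected full samples" of intervention and control communities.

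On the comparison of complementary subgroups (50/50 split, best case), the same text says that "the second-order contrast would have to be 30% in relative reduction, or 44 min. in abolute reduction". Table 10 prints 32% and 48 min for that row.

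**The concern.** With 9 degrees of freedom, t quantiles are clearly larger than normal ones. A table built with normal quantiles understates the effect that the planned t-test can detect at the stated power.

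Table 11 is the only statement of power for the binary secondary outcomes: reperfusion, in-hospital death, use of 911 and the outcomes from the telephone interviews. If its multiplier is wrong, every odds ratio and relative risk in it is too favourable. The closing summary of Section E, which calls power good for secondary outcomes of moderate prevalence, then rests on those figures.

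**Working it through.** **Inputs (Appendix C, Sections B and D, and Table 8).** J = 10 pairs; L = 1.5 yr; V_t = 459/1936 = 0.2371 yr²; K = 600, 400, 200 or 100 cases per community; best case R_β = 1.05 and ρ = 0.4; worst case R_β = 1.15 and ρ = 0. For binary outcomes σ_β = ln(R_β)/(2L).

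**Formulas.**
- SE² = 2σ_β²(1−ρ)/J + 2/[J·V_t·K·p(1−p)], with equal K in each community
- Δy = L × SE × m, and OR = exp(Δy)
- RR = √(p_Hi/p_Lo)
- m as prescribed (t, 9 df): 2.262 + 0.883 = 3.146
- m with normal quantiles: 1.960 + 0.842 = 2.802

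**The quoted figure (K = 600, p = 0.5, best case).**
- σ_β = ln(1.05)/3 = 0.01626, so the slope term is 2 × 0.0002645 × 0.6/10 = 0.0000317.
- The sampling term is 2/(10 × 0.2371 × 600 × 0.25) = 0.005624.
- SE = √0.005656 = 0.0752.
- Normal: Δy = 1.5 × 0.0752 × 2.802 = 0.316, so OR = 1.37 and RR = 1.17. These are the printed values.
- t on 9 df: Δy = 1.5 × 0.0752 × 3.146 = 0.355, so OR = 1.43 and RR = 1.19.

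In the worst case the normal multiplier gives OR 1.39 and RR 1.18, as printed. The t multiplier gives 1.44 and 1.20.

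**Other rows of Table 11, best case (OR / RR).**

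| K | Prevalence | Printed | Normal | t, 9 df |
|---|---|---|---|---|
| 600 | 1% | 4.87 / 4.76 | 4.87 / 4.76 | 5.92 / 5.76 |
| 600 | 5% | 2.06 / 1.98 | 2.06 / 1.98 | 2.25 / 2.15 |
| 600 | 10% | 1.69 / 1.60 | 1.69 / 1.60 | 1.80 / 1.70 |
| 600 | 20% | 1.48 / 1.37 | 1.48 / 1.37 | 1.56 / 1.42 |
| 600 | 30% | 1.41 / 1.27 | 1.41 / 1.27 | 1.47 / 1.31 |
| 400 | 50% | 1.47 / 1.21 | 1.47 / 1.21 | 1.54 / 1.24 |
| 200 | 50% | 1.73 / 1.31 | 1.73 / 1.31 | 1.85 / 1.36 |
| 100 | 10% | 3.62 / 3.10 | 3.62 / 3.10 | 4.24 / 3.54 |
| 100 | 50% | 2.16 / 1.47 | 2.16 / 1.47 | 2.38 / 1.54 |

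Over the whole table, 28 of 30 odds ratios and all 30 relative risks match the normal multiplier. None matches the t multiplier. The two exceptions are K = 400 at 5% (printed 2.48, computed 2.42) and K = 200 at 10% (printed 2.42, computed 2.48). Their relative risks and prevalence limits agree with the normal calculation, so the two odds ratios look interchanged.

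**The other tables.** The same check with σ = ½·log₁₀9:
- Table 5, K = 600, best case: printed 18% and 27 min (M = 2.5 hr). The t multiplier gives 17.8% and 26.7 min; the normal gives 16.0% and 24.0 min.
- Table 10, 50/50 split, best case: printed 32% and 48 min. The t multiplier gives 32.2% and 48.4 min; the normal gives 29.3% and 44.0 min.

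All rows of Table 5 and the best-case rows of Tables 9 and 10 follow the t multiplier. The sentence in the text on Table 10 gives 30% and 44 min, close to the normal result and not to the table.

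**Power at the Table 11 effects.** An effect set at 2.802 standard errors has noncentrality 2.802. The two-sided 5% t-test on 9 df then has power 0.704. At 3.146 standard errors the power is 0.799. Where the slope-variance term is negligible, closing the gap takes (3.146/2.802)² = 1.26 times as many cases per community.

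**The case against.** The strongest reply concerns consequence. Section X.A projects 750 usable cases per community, and Section X.C treats 600 as conservative and easily reached. With t quantiles and K = 750, the best-case odds ratios from 1% to 50% prevalence are 4.91, 2.07, 1.70, 1.49, 1.41 and 1.37, almost exactly those printed for K = 600. Power at the printed effects is then 79% to 80%. This is correct, but the table is labelled K = 600, and Appendix C, Section E calls that the expected size. It also does not help the 200- and 100-case rows, because those interview samples are fixed.

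Four smaller points have merit.
- The closing summary is qualitative and already excludes very high and very low prevalence. Part of it rests on Table 9, which used t quantiles.
- At 1% prevalence and K = 600 only about 6 events per community are expected (600 × 0.01), so the large-sample logistic variance is rough with either multiplier. The 5.92 is the protocol's own approximation with the right quantiles, not an exact figure.
- Table 9 has one stray entry: the worst case for a 1% subpopulation prints 88%, where the calculation and the table's own 129 min give 86%.
- The normal result for the Table 10 sentence is 29.3%, which rounds to 29% and not 30%. That the sentence came from a normal-quantile calculation is an inference; its contradiction with the table is plain.

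Section D does not restate the degrees of freedom. However, it uses the same t notation, and Appendix C gives no value other than 9.

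**Conclusion.** The point holds. Table 11 contradicts the formula printed above it and the test planned for these endpoints. At the tabulated sample sizes, the effects labelled as having 80% power have 70.4%, so the chance of missing them is about 30% instead of 20%.

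The understatement is small for common outcomes in the full sample and grows for rare outcomes and small samples: at K = 100 and 1% prevalence the odds ratio rises from 48.39 to 77.9. These figures assume the protocol's own variance model, equal K in each community, and the starting prevalence used in the variance, as Table 11 does. Power for the primary endpoint (Table 5) and the planned analyses are unaffected.

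**What to change.** 1. Recompute Table 11 with t quantiles on 9 df, and check the odds ratios for K = 400 at 5% and K = 200 at 10% when doing so. With the t multiplier they are 2.70 and 2.78.
2. In Appendix C, Section E, change the relative risks at 50% prevalence to 1.19 (best case) and 1.20 (worst case). Restate the figures for less common outcomes from the new table: about 1.7 at 10% prevalence and about 5.8 at 1%, for K = 600.
3. Bring the sentence on the 50/50 subgroup contrast into line with Table 10: 32% and 48 min.
4. Tie the closing statement on power for secondary outcomes to the recomputed values, keeping its restriction on prevalence. If the 750-case projection is the one relied on, add rows for K = 750 and say so.

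The cost is one recalculated table and a few sentences. Design, sample size and analysis stay as they are; the stated figures become somewhat less favourable.
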